#### 3.2.1.1. Additional Safety Endpoints of Interest

- Change from baseline in body weight at all post-dose time points as outlined in the SoA
- Percent change from baseline in body weight at all post-dose time points as outlined in the SoA
- Change from baseline in fasting plasma glucose at all post-dose time points as outlined in the SoA
- Change from baseline in HbA1c at all post-dose time points as outlined in the SoA

For these additional endpoints, baseline is defined as the last pre-dose measurement in Period 1 (i.e. Day -1).

#### 3.2.1.2. Laboratory Parameters of Interest – Liver Function Tests

Normalized values for liver function tests as described in Table 3 will be derived and a flag for each level of abnormality (ie "Flag Level" or "Alert Level") will be included in the derived dataset. If abnormalities persist across periods for the same participant these should be reported across the multiple periods.

Parameter	Flag Level	Alert Level	Conventional Units
Alanine	> ULN	-	U/L
aminotransferase	> 2x ULN	-	U/L
	> 3x ULN	-	U/L
	$> 5 \mathrm{X} \mathrm{ULN}$	> 8x ULN	U/L
	> 5x ULN	$> 10 \mathrm{x} \mathrm{ULN}$	U/L
	> 5x ULN	$> 20 \mathrm{x} \mathrm{ULN}$	U/L
Aspartate	> ULN	-	U/L
aminotransferase	> 2x ULN	-	U/L
	> 3x ULN	-	U/L
	> 5x ULN	> 8x ULN	U/L
	> 5x ULN	> 10x ULN	U/L
	> 5x ULN	$> 20 \mathrm{x} \mathrm{ULN}$	U/L
Alkaline	> 2x ULN	-	U/L
Phosphatase	> 3x ULN	-	U/L
1	> 5x ULN	-	U/L
Total Bilirubin	> 2x ULN	> 3x ULN	mg/dL
Direct and Indirect Bilirubin	> ULN	-	mg/dL

ULN – Upper Limit of Normal as determined by the central laboratory

#### 3.2.2. Assessment of Mental Health

• Assessment of mental health as determined by C-SSRS and PHQ-9 during the entire study.

#### 3.2.2.1. Columbia Suicide Severity Rating Scale (C-SSRS)

The C-SSRS is an interview-based rating scale to systematically assess suicidal ideation and suicidal behaviour.

Data relevant to the assessment of suicidality will be mapped to the Columbia-Classification Algorithm of Suicide Assessment (C-CASA) codes as given in Appendix 4.

#### **3.2.2.2.** Patient Health Questionnaire (PHQ-9)

The PHQ-9 is a 9 item self-report scale for the assessment of depressive symptoms. The PHQ-9 will be completed by participants and reviewed by site staff at the pre-defined time points outlined in the schedule of activities (SoA).

DMB02-GSOP-RF02 7.0 Statistical Analysis Plan Template 31-Jan-2022 PFIZER CONFIDENTIAL TMF Doc ID: 98.03 Page 11 of 30 The PHQ-9 total score will be derived for each time point separately by summing the responses to the 9 questions.

#### 3.2.3. Additional plasma PK Parameters for total Dabigatran and Rosuvastatin

- Additional plasma pharmacokinetic (*PK*) parameters for total dabigatran (Periods 1, 4 and 7: Cmax, Tmax, and CL/F, Vz/F, t2, as data permit
- Additional plasma pharmacokinetic (PK) parameters for rosuvastatin (Periods 2, 5 and 8): Cmax, Tmax, and CL/F, Vz/F, t1/2, as data permit

The additional plasma PK parameters for total dabigatran and rosuvastatin in Table 4 will be determined:

# Table 4. Summary of additional total dabigatran and rosuvastatin plasma PKParameters to be calculated

Parameter	Analysis Scale	Dabigatran Etexilate 150mg (Periods 1, 4 and 7)	Rosuvastatin 10mg (Periods 2, 5 and 8)
C max	Ln	A, D	A, D
T max	R	D	D
t1/2*	R	D	D
CL/F*	Ln	D	D
V z /F*	Ln	D	D

\*=if data permits. Abbreviations: A=analyzed using a statistical model; D=displayed with descriptive statistics as outlined in Table 8 in Section 6.2.2.1; ln=natural-log transformed; R=raw (untransformed).

#### 3.2.4. Plasma PK Parameters for PF-07081532

• *PF-07081532 plasma pharmacokinetic parameters* at Study Days 19 and 48: *AUC*24, *C*max, *T*max.

The plasma PK parameters for PF-07081532 in Table 5 will be determined:

Parameter	Analysis	PF-07081532 80mg QD	PF-07081532 240mg QD
	Scale	(Day 19)	(Day 48)
AUC 24	Ln	D	D
C max	Ln	D	D
$T_{max}$	R	D	D

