### CC

- k. Participants may undergo random urine drug testing at the discretion of the investigator.
- Assessments to be done on Day 1 of Periods 1, 3, and 5 and prior to IP administration on all days indicated.

Table 2. Overall Schedule of Activities Period 6 to ET

Visit Identifier Abbreviations used in this table may be found in Appendix 9			riod 6 81532 only	7)	Perio (PF-070) DI	81532 +	(PF-07	riod 8 7081532 + OSU)	F/U Visit q	F/U Contact Telephone	ET
Day in Study Period a	1-5	6-10	11-15	16-20	1-4	5	1-4	5	7-10	28-35	-
Days in Study b	24-28	29-33	34-38	39-43	44-47	48	49-52	53 f	59-62	80-87	-
Outpatient visit (after ≥10 hr fast)									X		
Physical exam											Χ°
Review contraception use - WOCBP Only (Section 5.3.1)									X	X	
Review drug, alcohol/tobacco use									X		
COVID-19 screening d											
C-SSRS and PHQ-9°	X			X				X	X		X
Review prior or concomitant treatments	$\rightarrow$	$\rightarrow$	$\rightarrow$	$\rightarrow$	_	<del>}</del>	$\rightarrow$	X	X	X	
AE monitoring	→	$\rightarrow$	$\rightarrow$	$\rightarrow$	_	>	$\rightarrow$	X	X	X	
Inpatient stay at CRU	→	$\rightarrow$	$\rightarrow$	$\rightarrow$	_	<del>}</del>	+	Xi			
Body weight g	X		X	X				Xi	X		X
Supine 12-lead ECG		Xh						$X^{i}$			X
Single, supine vital signs assessment	X		X	X				Xi	X		X
Blood Sampling for: k											
- Chemistry	X 			X 				X i	X		X
- Calcitonin, amylase, lipase				$X^1$				Xi			X
- Free T4, TSH, lipid panel, total bile acids								Xi	1		X
- Hematology/HbA1c				X 				Xi	X		X
- Serum pregnancy test m								Xi			
Rosuvastatin administration							Table 4				
DE administration					Table 3						
PF-07081532 administration n	→	→	→	→	1	Table 5	Table 4				
PF-07081532 PK						1					X
Rosuvastatin PK	Χ°						1	Table 4			
Dabigatran PK					Table 3						
CCI											
Urine Sampling for:											
- Urine drug test p											
- Urinalysis (and microscopy, as appropriate)											X

a. Day relative to start of dosing Day 1 of that Period.

b. Day relative to first dose of investigational product (DE) on Day 1 of Period 1.

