Study Day in Period					1					2	3°
Hours Relative to Dosing at 0 hr	0	0.5	1	2	3	4	6	8	12	24	48°
DE administration	Xª										
PF-07081532 administration (Periods 4 and 7 only)	Xª									X	X
Blood sampling for:b											
- Dabigatran (total) PK	X	X	X	X	X	X	X	X	X	X	X

- Dosing to occur with breakfast as specified in Section 6.1.1.
- Collection following fasting duration as specified in Section 5.3.2.
- c. There is no Day 3 in Period 1 and the 48-hour dabigatran PK sample in Period 1 is the same as the 0-hour sample in Period 2.

Table 4. Schedule of Activities – Period 2 (Rosuvastatin ONLY), Period 5 (Rosuvastatin + PF07081532 80 mg QD), and Period 8 (Rosuvastatin + PF-07081532 260 mg QD)

Study Day in Period						l					2	3	4	5
Hours Relative to Dosing at 0 hr	0	1	2	3	4	5	6	8	10	14	24	48	72	96°
Rosuvastatin administration	Xa													
PF-07081532 administration (Periods 5 and 8 only)	Xª										X	X	X	
Blood sampling for:b														
- Rosuvastatin PK	X	X	X	X	X	X	X	X	X	X	X	X	X	X
- Dabigatran (total) PK (Period 2 only)	Xd													
CCI														
- PF-07081532 PK (Periods 5 and 8 only)	X°													

- Dosing to occur with breakfast as specified in Section 6.1.1.
- Collection following fasting duration as specified in Section 5.3.2.
- c. The 96-hour PK rosuvastatin samples in Periods 2 and 5 are the same as the 0-hour PK samples on Day 1 in Periods 3 and 6, respectively.
- d. For Period 2 only, the 0-hr dabigatran PK sample is the same as the 48-hr PK sample from Period 1.
- e. The 0-hr PF-07081532 PK samples in Periods 5 and 8 are the same as the 24-hr PK samples from Day 5 of Periods 4 and 7, respectively.

Table 5. Schedule of Activities – Day 5 of Period 4 (DE + PF-07081532 80 mg QD) and Period 7 (DE + PF-07081532 260 mg QD)

Study Day in Period		5								
Hours Relative to Dosing at 0 hr	0	0.5	1	2	4	6	8	10	14	24°
PF-07081532 administration	Xa									
Blood sampling for:b										
- PF-07081532 PK	X	X	X	X	X	X	X	X	X	X

a. Dosing to occur with breakfast as specified in Section 6.1.1.

b. Collection following fasting duration as specified in Section 5.3.2.

c. Note: the 24-hour samples for Period 4 Day 5 and Period 7 Day 5 are the same as the 0-hour samples in Period 5 Day 1 and Period 8 Day 1, respectively.

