#### 6.1.1. Administration

Following an overnight fast of at least 10 hours, participants will receive PF-07081532 with the breakfast meal at approximately 0800 hours (±2 hours). Investigator site personnel will administer PF-07081532, rosuvastatin, or DE during each period (as applicable per SoA) with ambient temperature water to a total volume of approximately 240 mL. Participants will swallow the study intervention whole and will not manipulate or chew the study intervention prior to swallowing. The study intervention will be administered according to the IP manual.

PF-07081532 must be administered within approximately 10 minutes of completion of the morning meal (Periods 3 through 8).

During the dabigatran DDI assessment periods (Periods 4 and 7), PF-07081532 will be administered first followed by administration of DE approximately 60 minutes later. When DE is administered alone (Period 1), it must be administered approximately 60 minutes after completion of the morning meal.

During the rosuvastatin DDI assessment periods (Periods 5 and 8), PF-07081532 will be administered first and rosuvastatin will be administered approximately 10 minutes later. When rosuvastatin is administered alone (Period 2), it must be administered within approximately 10 minutes of completion of the morning meal.

In order to standardize the conditions on PK sampling days, all participants will be required to refrain from lying down (except when required for BP, pulse rate, and ECG measurements), eating, and drinking beverages other than water during the first 4 hours after dosing.

Administration of study intervention will occur according to the study periods and dosing days listed in the SoA and Table 8.

**Table 8.** Study Interventions Administered

Study Period	Study Day	Drug and Dosage
Period 1, Days 1-2	1-2	SD DE 150 mg
Period 2, Days 1-4	3-6	SD Rosuvastatin 10 mg
Period 3, Days 1-4	7-10	PF-07081532 20 mg QD
Period 3, Days 5-8	11-14	PF-07081532 40 mg QD
Period 4, Days 1-5	15-19	PF-07081532 80 mg QD + SD DE 150 mg
Period 5, Days 1-4	20-23	PF-07081532 80 mg QD + SD Rosuvastatin 10 mg

**Table 8.** Study Interventions Administered

Study Period	Study Day	Drug and Dosage
Period 6, Days 1-4	24-27	PF-07081532 120 mg QD
Period 6, Days 5-8	28-31	PF-07081532 160 mg QD
Period 6, Days 9-12	32-35	PF-07081532 200 mg QD
Period 6, Days 13-16	36-39	PF-07081532 220 mg QD
Period 6, Days 17-20	40-43	PF-07081532 240 mg QD
Period 7, Days 1-5	44-48	PF-07081532 260 mg QD + SD DE 150 mg

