Period 8, Days 1-5*	49-53*	PF-07081532 260 mg QD + SD Rosuvastatin 10 mg

\*No drug administration in Period 8, Day 5 (Study Day 53); participants discharged from the CRU.

Modification of PF-07081532 dosing may be permitted **upon sponsor approval only** (see Section 6.6).

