# 2.1. Modifications to the Analysis Plan Described in the Protocol

Due to the dosing of PF-07081532 being capped at 240mg QD, the titration of PF-07081532 stopped at the end of Period 6 and the study was shortened by 6 days. Therefore, the study design presented in Section 2.3 is accurate according to study protocol but not the most up to date study design for C3991047, in terms of dose and execution day.

DMB02-GSOP-RF02 7.0 Statistical Analysis Plan Template 31-Jan-2022 PFIZER CONFIDENTIAL TMF Doc ID: 98.03 Page 6 of 30

	Objective	Endpoint
	Primary:	Primary:
PK Section 6.1	• To estimate the effect of PF-07081532 administration on the single-dose PK of total dabigatran in otherwise healthy overweight or obese participants.	• Dabigatran (total) PK parameters: AUC inf (if data permit* otherwise AUC last ) in Periods 1, 4, and 7.
PK Section 6.1	• To estimate the effect of MD PF- 07081532 on the single-dose PK of rosuvastatin in otherwise healthy overweight or obese participants.	• Rosuvastatin PK parameters: AUC inf (if data permit* otherwise AUC last ) in Periods 2, 5, and 8.
	Secondary:	Secondary:
Safety Section 6.2	• To evaluate the safety and tolerability of PF-07081532 administered separately and in combination with DE in otherwise healthy overweight or obese participants.	
 
Assessment of TEAEs, clinical laboratory abnormalities, vital signs, body weight, and ECG parameters.
 
Assessment of mental health as determined by C-SSRS and PHQ-9.
 

Safety Section 6.2	• To evaluate the safety and tolerability of PF-07081532 administered separately and in combination with rosuvastatin in otherwise healthy overweight or obese participants	
 
Assessment of TEAEs, clinical laboratory abnormalities, vital signs, body weight, and ECG parameters.
 
Assessment of mental health as determined by C-SSRS and PHQ-9.
 

PK Section 6.2.2.1	• To evaluate the effects of PF-07081532 on additional PK parameters for total dabigatran.	• Additional plasma PK parameters for total dabigatran: C max and T max ; and CL/F, V z /F, t 2 as data permit, in Periods 1, 4, and 7.
PK Section 6.2.2.1	• To evaluate the effects of PF-07081532 on additional PK parameters for rosuvastatin.	• Additional plasma PK parameters for rosuvastatin: C max and T max ; and CL/F, V z /F, t 1/2 as data permit, in Periods 2, 5, and 8.

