# 6.2.2.2. Plasma PK Parameters for PF-07081532

Plasma PK parameters for PF-07081532 as described in Section 3.2.4 will be listed and summarized descriptively for participants in the PK Parameter Set (as defined in Section 4). Missing values will be handled as detailed in Section 5.3.

AUC24,  $C_{max}$ ,  $T_{max}$  will be summarized for each treatment period of PF-07081532 as required in the table below:

Parameter	Summary Statistics
AUC 24 , C max	N, arithmetic mean, median, cv%, standard deviation, minimum, maximum, geometric mean and geometric cv%.
T max	N, median, minimum, maximum.
DMB02-GSOP-RF02 7.0 Statistical Analysis Plan Template 31-Jan-2022	
PFIZER CONFIDENTIAL	
TMF Doc ID: 98.03	
Page 22 of 30	

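### Does the Study Day 48 label for the 240 mg PF-07081532 profile, which fits only the unshortened schedule, require a change to the SAP?

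*SAP*

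**What the plan says.** SAP 3.2.4 defines AUC24, Cmax and Tmax of PF-07081532 "at Study Days 19 and 48". SAP Table 5 heads its columns 80 mg QD (Day 19) and 240 mg QD (Day 48). SAP 6.2.2.2 refers back to this definition: "Plasma PK parameters for PF-07081532 as described in Section 3.2.4 will be listed and summarized descriptively".

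SAP 2.1 says that dosing was capped at 240 mg QD and that "the titration of PF-07081532 stopped at the end of Period 6 and the study was shortened by 6 days". It describes the design in Section 2.3 as "accurate according to study protocol but not the most up to date study design for C3991047, in terms of dose and execution day". It names no other section. SAP 2.3 shows 240 mg in Periods 6 to 8 and keeps the 54-day inpatient layout.

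The protocol counts study days as "Day relative to first dose of investigational product (DE) on Day 1 of Period 1" (Schedule of Activities, Table 2, note b). Protocol Table 8 gives Period 7 as Days 44 to 48, with "PF-07081532 260 mg QD + SD DE 150 mg". Its footnote reads "No drug administration in Period 8, Day 5 (Study Day 53); participants discharged from the CRU". Protocol Table 5 sets serial PF-07081532 sampling on Day 5 of Periods 4 and 7, and its note c says that "the 24-hour samples for Period 4 Day 5 and Period 7 Day 5 are the same as the 0-hour samples" on Day 1 of Periods 5 and 8.

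**The concern.** The column in SAP Table 5 appears to pair the capped dose with a day from the uncapped calendar. If six inpatient days were dropped, Day 48 falls after discharge, when no PF-07081532 sample is scheduled. An endpoint definition would then name a day on which the measurement could not have been made. The caveat in 2.1 does not help directly, because it mentions only Section 2.3. That caveat is also loose: on dose, 2.3 departs from the protocol and already shows the cap, so it is neither faithful to the protocol nor out of date.

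At stake would be a mis-specified secondary endpoint. A program that selected records by study day could miss the high-dose profile, and a reader could be unsure which dose and day the reported exposure belongs to.

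**Working it through.** **Inputs.** Period lengths are from Protocol 4.1, with Period 1 counted from Day 1 (Day -1 left out): 2, 4, 8, 5, 4, 20, 5, 5. The cut of 6 days is from SAP 2.1. Follow-up is 7 to 10 days after the last dose (Protocol 4.1, SAP 2.3).

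**Reproducing the SAP's days.**
- Period 4 Day 5: 2 + 4 + 8 + 5 = Day 19.
- Period 7 Day 5: 19 + 4 + 20 + 5 = Day 48.
- Discharge: 48 + 5 = Day 53; last dose Day 52. With Day -1 the stay is 54 days.

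Both SAP days match the protocol's full calendar exactly.

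**Removing six inpatient days.** This is an assumption. It fits 2.1, which ties the shortening to the dose cap.
- Last dose: 52 - 6 = Day 46.
- Discharge: 53 - 6 = Day 47.
- First follow-up: 46 + 7 = Day 53 to 46 + 10 = Day 56.
- Day 48 is therefore one day after discharge and five days before the follow-up window opens.

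**Where the profile would fall.** If k of the six days came out after the profile, its day is 48 - (6 - k). For k = 0 this is Day 42, and for k = 1 to 5 it is Days 43 to 47. If Period 8 keeps its five days, it runs from Day 43 to Day 47. Its Day 1 pre-dose sample closes the Period 7 profile, which puts the profile on Day 42. The documents do not say where the days were taken out, so Day 42 is conditional. Day 48 is excluded in every case. Day 19 stands if the cut came after Period 5.

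**What the analysis text uses.**
- SAP 6.2.2.2 summarises AUC24, Cmax and Tmax for each PF-07081532 treatment period. The listings, concentration summaries and plots are likewise by treatment period.
- The opening of SAP 6 makes study day mean day within a period unless otherwise specified. No period has 48 days, so Day 48 can only be the protocol's running count.
- SAP 5.2 presents results by period and labels Period 7 as 240 mg QD.
- SAP 3 takes sampling from the protocol's schedule, and SAP 5.3.1 derives parameters from actual sampling times.

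The schedule gives one serial PF-07081532 profile in Period 7. Period, not the day number, identifies it.

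**The dose wording.** Protocol 4.1 has 260 mg in Periods 7 and 8; SAP 2.3 has 240 mg. The SAP's version history and 2.1 both record the cap, and 240 mg is used throughout SAP 2.3, 3.2.4, 5.2, 6.1.1 and 6.2.2.1. The treatment labels in the analysis therefore agree with one another.

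**The case for a change.** The best argument for amending is that SAP 2.1 exists to reconcile the plan with what was done. Version 2 changed the dose in 3.2.4 but left the day, so an endpoint definition contradicts the SAP's own account of the study. No other clause makes Day 48 right, 6.2.2.2 points back to it, and 2.1 is wrong about 2.3 on dose. The repair would cost only a few words.

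All of those facts stand. What does not follow is a consequence for the analysis. The risk needs a program that selects on the running study day, and no document describes one. Such a filter would return no profile for the whole high-dose column, which would be noticed at once and would not bias a number. SAP 2.1 also tells the reader that the day layout has moved, so what is missing is in effect a cross-reference to 3.2.4. The executed days may be on file elsewhere: Protocol 8.5 has changes to assessment timing documented in the study files without an amendment.

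**Conclusion.** No change to the plan follows. The Day 48 label is a clerical leftover, and the description of Section 2.3 in SAP 2.1 is loosely worded. The day label is out by 6 days if the whole cut preceded the profile, and by 1 to 5 days otherwise. Its effect on results is nil: the endpoint is secondary and descriptive, it is summarised by period, and the profile remains identifiable. The dabigatran and rosuvastatin comparisons do not use this day.

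The finding that Day 48 cannot be right rests on the six days being inpatient days. Day 42 further requires that Period 8 kept its five days. The dose statements in Protocol 4.1, SAP 2.1 and SAP 2.3 differ and should be read together with the SAP's version history; no view is taken here on which dose is right.

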#### Table 5. Summary of PF-07081532 plasma PK Parameters to be calculated

Abbreviations: D=displayed with descriptive statistics as outlined in Table 9 in Section 6.2.2.2; ln=natural-log transformed; R=raw (untransformed).

## **3.3. Other Endpoint(s)**

CCI		

**3.4. Baseline Variables** Not applicable.

# 3.5. Safety Endpoints

See Section 3.2 for details.

DMB02-GSOP-RF02 7.0 Statistical Analysis Plan Template 31-Jan-2022 PFIZER CONFIDENTIAL TMF Doc ID: 98.03 Page 13 of 30

## 4. ANALYSIS SETS (POPULATIONS FOR ANALYSIS)

Data for all participants will be assessed to determine if participants meet the criteria for inclusion in each analysis population prior to unblinding and releasing the database and classifications will be documented per standard operating procedures.

Participant Analysis Set	Description
Enrolled	"Enrolled" means a participant's, or their legally authorized representative's, agreement to participate in a clinical study following completion of the informed consent process and assignment to study intervention. A participant will be considered enrolled if the informed consent is not withdrawn prior to participating in any study activity after screening. Potential participants who are screened for the purpose of determining eligibility for the study, but do not participate in the study, are not considered enrolled, unless otherwise specified by the protocol.
Evaluable	All participants assigned to study intervention and who take at least 1 dose of study intervention.
Safety analysis set	All participants randomly assigned to study intervention and who take at least 1 dose of study intervention.
PK Concentration Set	The PK concentration population is defined as all participants who receive at least 1 dose of rosuvastatin, dabigatran etexilate, and/or PF-07081532 and in whom at least 1 plasma concentration value is reported
PK Parameter Set	The PK parameter analysis population is defined as all participants who receive at least 1 dose of rosuvastatin, dabigatran etexilate, and/or PF-07081532 and have at least 1 of the PK parameters of interest calculated. Should vomiting occur after co-administration of rosuvastatin or dabigatran etexilate with PF-07081532, the resulting PK parameters from that participant from the corresponding period may be excluded, where further details are provided in Section 5.3.

## **5. GENERAL METHODOLOGY AND CONVENTIONS**

#### 5.1. Hypotheses and Decision Rules

There is no statistical hypothesis testing planned for this study and no statistical decision rules will be applied.

#### 5.2. General Methods

Unless otherwise stated, all summaries and plots will be presented by treatment group (equivalent to 'by Period'). The following treatment labels (or similar) will be used, which represent Periods 1 to 8 as:

Period	Treatment Label
1	Dabigatran etexilate 150 mg (Period 1)
2	Rosuvastatin 10 mg (Period 2)
3	PF-07081532 titration up to 40 mg QD (Period 3)
4	PF-07081532 80 mg QD + dabigatran etexilate 150 mg (Period 4)
5	PF-07081532 80 mg QD + rosuvastatin 10 mg (Period 5)
6	PF-07081532 titration up to 240 mg QD (Period 6)
7	PF-07081532 240 mg QD + dabigatran etexilate 150 mg (Period 7)
8	PF-07081532 240 mg QD + rosuvastatin 10 mg (Period 8)

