## 6.5. Study Intervention Compliance

When the individual dose for a participant is prepared from a bulk supply, the preparation of the dose will be confirmed by a second qualified member of the study site staff.

When participants are dosed at the site, they will receive study intervention directly from the investigator or designee, under medical supervision. The date and time of each dose

administered in the clinic will be recorded in the source documents and recorded in the CRF. The dose of study intervention and study participant identification will be confirmed at the time of dosing by a member of the study site staff other than the person administering the study intervention.

Study site personnel will examine each participant's mouth to ensure that the study intervention was ingested; this is vitally important to ensure dosing compliance in light of the potential gastrointestinal AEs. Additionally, if vomiting occurs following oral dosing and up to 4 hours post-dose (twice the median Tmax of PF-07081532), site personnel will examine the emesis for evidence of drug product.

A record of the number of PF-07081532 and rosuvastatin tablets and dabigatran capsules dispensed to and taken by each participant must be maintained and reconciled with study intervention and compliance records. Intervention start and stop dates, including dates for intervention delays and/or dose reductions, will also be recorded in the CRF.

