#### 6.6. Dose Modification

Based on emerging data from other clinical studies that may become available during the conduct of this study, the titration rate, incremental increases in dose, and/or the PF-07081532 doses at which rosuvastatin or the dabigatran PK interactions are evaluated may be adjusted. If participants are not able to tolerate titration to higher doses of PF-07081532 (eg, ≥180 mg QD), titration to the next dose level may be delayed temporarily or titration to a maximum tolerated dose may be permitted, with sponsor approval only.

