#### **1. VERSION HISTORY**

Version/	Associated	Rationale	Specific Changes
Date	Protocol		
	Amendment		
1	Original	N/A	N/A
24 Mar 2023	31 Jan 2023		
2 04 Jul 2023	N/A	In order to be consistent with C3991004 IRC Charter (01-May-2023) inclusion of LFTs outputs.	Addition of Sections 3.2.1.2 and 6.2.1.2.1 describing additional outputs related to LFTs to be reported and the expected outputs.
		Dosing of PF- 07081532 was capped at 240mg QD.	Addition of text to Section 2.1 to explain the change of design from the protocol.
		Changes to vital signs thresholds to include a maximum threshold for SBP and DBP	Changes to Appendix 2 – Categories for Vital Signs
		These definitions of baseline were not being used in any analyses	Removal of the definitions of baseline for C-SSRS and PHQ-9
		Analyses are not needed as sufficient participants got to 240mg QD	Removed sensitivity analysis for Section 6.1.1

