#### 6.5.3. Study Treatment Exposure

Not applicable.

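### The Period 7 and 8 safety columns labelled 240 mg QD can include participants who were taking less, and the SAP plans no exposure summary that would show it

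*SAP*

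**What the plan says.** SAP 5.2 sets the reporting unit: unless a section says otherwise, "all summaries and plots will be presented by treatment group (equivalent to 'by Period". The last three treatment labels are "PF-07081532 titration up to 240 mg QD (Period 6", "PF-07081532 240 mg QD + dabigatran etexilate 150 mg (Period 7" and "PF-07081532 240 mg QD + rosuvastatin 10 mg (Period 8".

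Protocol 6.6 provides that, for participants who cannot tolerate higher doses, "titration to the next dose level may be delayed temporarily or titration to a maximum tolerated dose may be permitted, with sponsor approval only".

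SAP 6.1.1 anticipates this for PK. If a participant misses the target dose by the end of Period 3 or 6, the dabigatran and rosuvastatin parameters from the periods that follow stay out of the mixed models.

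The safety sections (SAP 6.2.1.1 to 6.2.1.8) contain no such rule. The section "Study Treatment Exposure" (SAP 6.5.3) is marked not applicable.

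The SAP version history explains why a PK sensitivity analysis was dropped: "Analyses are not needed as sufficient participants got to 240mg QD".

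Protocol 6.5 shows that the data exist: "Intervention start and stop dates, including dates for intervention delays and/or dose reductions, will also be recorded in the CRF".

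**The concern.** Safety and tolerability of PF-07081532, alone and in combination, are secondary objectives. A reader of the study report will take a column headed 240 mg QD as describing people on 240 mg QD. Under the protocol, someone can be in Period 7 or 8 on a lower dose without having deviated or discontinued. The plan counts that person under the label. Those held back are selected for how they tolerated titration, so their event rate need not match the rest of the column.

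The SAP already treats such participants as different enough to remove from the PK models. It then leaves them unmarked in the safety tables and plans no summary of the dose actually taken.

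**Working it through.** **1. Can a participant be in Period 7 or 8 below 240 mg?** Protocol 6.6 allows a delay or a lower maximum tolerated dose. SAP 6.1.1 provides for PK parameters from the later periods of participants who missed the target, so it presupposes that they continue. The version history says that enough participants reached 240 mg. It does not say that all did, and it gives no count.

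**2. Which planned outputs would show it?**
- Dabigatran and rosuvastatin models: handled by exclusion (SAP 6.1.1).
- AE, laboratory, vital sign, ECG, weight and questionnaire summaries: by treatment, meaning period, with no rule on dose taken.
- Safety analysis set: anyone with at least one dose (SAP 4).
- Disposition: counts discontinuations (SAP 6.5.2). A participant held at a lower dose has not discontinued.
- Exposure: none planned (SAP 6.5.3).

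**3. How large could the effect be?** Let n be the participants in the column, k those below 240 mg, and p_240 and p_low the AE incidences in the two groups.
- Printed incidence = [(n − k) × p_240 + k × p_low] / n.
- Departure from p_240 = (k/n) × (p_low − p_240).

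The documents give 24 enrolled and about 16 evaluable completers. They do not give k, so 1 to 8 is an assumption.
- n = 24: 1/24 = 4% to 8/24 = 33% of the column.
- n = 16: 1/16 = 6% to 8/16 = 50% of the column.

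Take incidences of 50% and 20% purely as an illustration, a gap of 30 points:
- n = 24, k = 8, p_240 = 50%, p_low = 20%: (16 × 0.5 + 8 × 0.2)/24 = 0.40, which is 10 points too low.
- Rates swapped: (16 × 0.2 + 8 × 0.5)/24 = 0.30, which is 10 points too high.
- k = 1: 30/24 = 1.25 points for n = 24 and 30/16 = 1.9 points for n = 16, in either direction.
- n = 16, k = 8: 0.5 × 30 = 15 points, in either direction.

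**4. What does Period 6 pool?** Protocol Table 8 gives 120, 160, 200, 220 and 240 mg for 4 days each: 5 × 4 = 20 days, which matches the 20 days in SAP 2.3. Days planned at 240 mg: 4/20 = 20%. Day-weighted mean: (120 + 160 + 200 + 220 + 240)/5 = 188 mg. The pooling affects outputs differently:
- AEs are collected continuously, so all five levels fall in one column. The same holds for unplanned measurements and for maximum or minimum categories.
- The scheduled ECG is on Day 10 (planned 200 mg).
- Vital signs and weight are on Days 5, 12 and 19. The vital signs are pre-dose, so they follow planned doses of 120, 200 and 240 mg. These summaries are also split by time point.
- Hematology, calcitonin, amylase and lipase are on Day 20 (planned 240 mg).

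**5. Would liver-test flags by dose level be informative?** From the first PF-07081532 dose to discharge, chemistry is scheduled on Period 3 Day 8 (40 mg), Period 6 Days 1 and 20, and Period 8 Day 5. SAP 6.2.1.2 attributes a pre-dose Day 1 abnormality to the previous period, here Period 5 at 80 mg. No scheduled sample falls at 20, 160, 200 or 220 mg, and none at 120 mg if the Period 6 Day 1 sample is pre-dose.

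**The case against.** The strongest reply is that this is a presentation choice for descriptive secondary data. No hypothesis is tested, no objective asks for tolerability by dose, sponsor approval is needed to stay at a lower dose, and the cap removed the planned 260 mg step. The number below 240 mg could be nil. AE, laboratory, vital sign and ECG outputs also follow sponsor reporting standards that are not in these documents and might show dose. All of this stands as a limit on size. None of it puts an exposure summary or an off-label-dose count into the plan.

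A second reply concerns Period 6. A reader might infer that its column is mislabelled and that nothing in it can be read by dose. The documents do not support that: the label openly says titration, and vital signs, ECG, weight and questionnaires are also summarized by time point. What remains for Period 6 is mainly the AE output.

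A third reply is that tables by dose would not support dose comparisons. This is correct. The sequence is fixed with no washout, so dose rises with time on drug however the columns are cut. The case for actual-dose reporting is correct labelling, not a dose-response estimate.

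**Conclusion.** The gap is real and limited. Following the SAP as written, the Period 7 and 8 columns headed 240 mg QD can include participants who were not taking 240 mg, and no planned summary would reveal how many. The share is unknown; 4% to 50% is the span of an assumed 1 to 8 participants over columns of 24 or 16.

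Two stronger readings should be resisted. A reader might infer that incidence at 240 mg is understated or overstated. The documents give neither the count nor the event rates, and participants held lower could have more events or fewer. A reader might also infer that the drug-interaction results are contaminated. They are not, because SAP 6.1.1 keeps those parameters out of the primary models.

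The five-level description of Period 6 rests on protocol Table 8. SAP 2.1 says that the study was shortened by 6 days and that its design text is not current for dose and execution day, so the executed schedule cannot be confirmed. That adds to the case for reporting actual exposure. This is an inexpensive reporting improvement, worth making.

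**What to change.** - **SAP 6.5.3:** replace the not-applicable entry with a table, for the safety analysis set, of participants and participant-days at each actual PF-07081532 dose, by period.
- **Period 7 and 8 safety tables:** state in each column header or footnote the number of participants not on the labelled dose. Define this from CRF dosing records, for example any dosing day in the period with a recorded dose below 240 mg. Show TEAEs for those on the labelled dose separately from those below it.
- **Period 6:** add the actual dose at onset to the TEAE output.
- **Liver tests:** a full table of flags at all eight dose levels is not needed, because scheduled chemistry misses most levels.

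The cost is SAP wording, one exposure table, footnotes, one split of the TEAE tables and one added item, all from data already collected. No dosing rule changes. If nobody was below 240 mg, the footnote reads zero, the label is verified and the split falls away. The downside is small denominators in descriptive tables, which should carry a note that dose is confounded with time on drug.
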